plans and actions for well-woman, primary and/or specialty care, and implementation outcomes, including opinions of and satisfaction with postpartum care and the planning process. The 14-month survey will assess well-woman, primary and specialty care use, contraceptive use, perceived cardiovascular risks, mental well-being (depression²¹ and social support²²), and self-rated health.²⁵ (See the 12-week survey and 14-month survey documents for more information.) The survey will also validate EMR information on hospital readmission, SMM, and medication adherence.

To promote retention of participants over the 14-month follow-up period, we will ask participants to provide at least three ways to contact them (e.g., email addresses, own phone number, or phone number of a partner or family member). Upon completing the 12-week survey, the research team will confirm the preferred contact information for the 14-month survey.

Medical chart review will be used to ascertain health care utilization (postpartum visit, primary care or specialty care utilization, hospital admissions), diagnoses, and medical prescriptions in the 12 months postpartum. A standardized medical abstraction form will be used by research team members who have trained in data abstraction from the medical record. If additional medical records are available from care obtained outside of Grady, that information will also be reviewed and abstracted. The primary outcome of interest (4–12-week postpartum visit attendance) will be identified using data from the medical record. Information on all outpatient visits occurring between delivery discharge and 12 weeks postpartum will be abstracted and blinded for review. Two independent physicians will review the blinded information and determine whether the visit meets the criteria for a comprehensive postpartum visit. ER and urgent care visits external to Grady that fall within the 4 – 12-week postpartum period and through 14 months postpartum will be abstracted but not blinded for review by the blinded reviewers. Information for these visit types occurring within Grady Health System during these time periods will be obtained from the “GOGO” data warehouse (IRB00103211). Mobile integrated health visits, triage visits, and nurse visits occurring during these time periods will not be abstracted or blinded.

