Once the study results are publicly disseminated, we will inform the study participants via text, email, or telephone, depending on their preferred means of contact. Aim 2 participants with an active account will be able to view the postpartum plan via MyChart. For participants without an active MyChart account, the postpartum plan will be printed for them. We will work with the Community Advisory Board for this study to disseminate results broadly to the communities served by Grady.

9. Study Timelines

Aim 1: Each in-depth interview is expected to last approximately 30 minutes. Each participant will be interviewed only once. We anticipate that it will take approximately one month to enroll all interview participants. We estimate that the qualitative data will be analyzed by the end of Year 1.

Aim 2: Individuals will participate in the study for approximately 18 months (starting during prenatal care and continuing 14 months after delivery). There are approximately 200 deliveries per month at Grady. Assuming that 40% of women will be eligible (data

Protocol Title: Minding the gap: improving women's health through coordinated postpartum planning

from our study suggests that 38% of women at Grady have hypertensive disorders²⁶⁾ and about 15% of women will not receive any prenatal care, and 50% will agree to participate in the study, we expect recruitment to take about 9 months. We estimate that data from the randomized trial will be analyzed during Year 5.

RCT Pilot: The piloting will be iterative and will occur between May and July 2022.

Study Timeline

	Year 1				Year 2				Year 3				Year 4				Year 5			
	1	2	3	4	1	2	3	4	1	2	3	4	1	2	3	4	1	2	3	4
Project launch	1																			
1 Develop questions for interviews		1																		
1 Conduct interviews			1																	
1 Analyze qualitative data				1																
2 Develop content for care system					1															
2 Design and test EMR tool						1														
2 Study start up							1													
2 Enroll women								1												
2 Follow women for 14 months									1											
2 Conduct follow-up surveys										1										
Analyze/disseminate RCT results											1									
Prepare manuscripts												1								

10. Inclusion and Exclusion Criteria

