therefore warrant inclusion in the study. We are requesting a waiver of parental consent for pregnant women <18 years of age. Requesting a parental waiver will not adversely affect the rights and welfare of the participants as teens will already be visiting the clinic for prenatal care. Also, requiring parental consent offers no additional protection to the participant. Participants <18 years of age will receive the same information about the study as participants 18 years of age and over. We will use an under 18 informed consent form in the place of the assent process for participants >18 years, since these participants will be in the upper age group for minor subjects. If the participant does not appear to comprehend the consent form or the research, they will not be enrolled. If a participant < 18 years turns 18 during the study period, they will be invited to complete the full informed consent at that time.

RCT Pilot: The pilot involves medical records for pregnant women (same eligibility criteria for Aim 2). Review of patient medical records will in no way modify the clinical care the participants receive during and after their pregnancy.

12. Local Number of Participants

Aim 1: We will recruit up to 30 women.

Aim 2: We will recruit 320 women. Based on prior studies at Grady, we assume a recruitment rate of 50% and expect to approach approximately 640 women.

RCT Pilot: We will review the minimum number of records to finalize instruments, likely between 5-10 records.

13. Recruitment Methods

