Participants in this research study may not receive any benefit. However, participants in the intervention arm of the study may benefit from better continuity of care, more one on one time with a provider during prenatal care, and enhanced follow-up postpartum. In addition, the potential benefits of this research may extend to future postpartum patients at Grady Memorial Hospital or in other communities as these data are incorporated into the design of an EMR-integrated, culturally appropriate postpartum planning system.

17. Data Management and Confidentiality

Aim 1: All qualitative data will be professionally transcribed. These transcripts will be cleaned and de-identified prior to analysis. Once cleaned, we will use a team-based approach to systematically code each transcript using a qualitative software program called MaxQDA2020. Two researchers will review and code the transcripts with a lead analyst to identify emerging themes. We will use a directed approach to content analysis whereby the research theory will be used as guidance for data coding.

Aim 2: For Aim 2, we will conduct a randomized controlled trial to test the effectiveness of the comprehensive postpartum care system on postpartum care use and engagement. The primary outcome will be attendance at the postpartum visit occurring between 4-12 weeks after delivery. Secondary outcomes include receipt of early postpartum screenings for diabetes and hypertension (e.g., glucose testing or blood pressure checks), contraceptive initiation and use, use of medication for chronic conditions, pregnancy complications (including severe maternal morbidity), hospital readmissions, mental health status, perceived risks for SMM and cardiovascular disease, care plans and use, and satisfaction with care.

We will recruit 320 pregnant women between 20-34 weeks of gestation who receive 1 or more prenatal care visits in the Grady OB/GYN clinic, intend to deliver at Grady Memorial Hospital, have a documented diagnosis of chronic diabetes, chronic hypertension, pre-pregnancy obesity, gestational diabetes, and/or HDP and speak English or Spanish. We will assign participants to intervention or control arm using simple randomization. Participants will be randomized (1:1) to receive the postpartum care system (175) or standard of care (175) and will be followed for up to 14 months to allow ample time for attending the 4–12-week postpartum visit and to connect to primary and specialty care.

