Power. Preliminary data suggest that 55% of women with HDP return for a postpartum follow-up visit in the absence of the intervention. Based on this, we should have 80% power to detect

Protocol Title: Minding the gap: improving women's health through coordinated postpartum planning

a risk ratio of 1.5 (or greater) with a sample of 292 women (146 in each arm), stratified evenly by chronic or new onset disease. To achieve this, 78% of women in the intervention arm would need to attend the postpartum visit, which is conservative. Assuming some (up to 15%) loss to follow-up, we should aim to recruit a sample of 320 women.

Analysis.

Primary outcome (Attendance at 4–12-week postpartum visit): We will compare the probability of attending the 4–12-week postpartum visit between intervention and control groups. We will fit log binomial models to estimate the effect (risk difference and relative risk) of the intervention on attendance at the 4–12-week visit, adjusting for diagnosis (chronic hypertension, chronic diabetes, pre-pregnancy obesity, gestational diabetes, or hypertensive disorder of pregnancy). If sample size permits, we will include relevant confounders, as appropriate.

Secondary outcomes: Secondary outcomes include receipt of recommended early postpartum screenings for diabetes and hypertension (e.g., glucose testing or blood pressure checks), contraceptive initiation and use, use of medication for chronic conditions, pregnancy complications (including SMM), hospital readmissions, mental health status, perceived risks for SMM and cardiovascular disease, plans for and use of primary and specialty care, and satisfaction with postpartum care. We will analyze these outcomes using log-binomial models to estimate relative risks and risk differences and 95% confidence intervals, adjusting diagnosis.

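### The recruitment target of 320 does not follow from 292 evaluable women with up to 15% loss (that needs 344), and the stated arms of 175 + 175 = 350 contradict it

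*Combined protocol and SAP*

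**What the plan says.** All references are to the combined protocol and SAP.

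- **Section 17, Power.** The stated power is claimed "with a sample of 292 women (146 in each arm), stratified evenly by chronic or new onset disease", for 55% attendance without the intervention against 78% with it. The recruitment target follows at once: "Assuming some (up to 15%) loss to follow-up, we should aim to recruit a sample of 320 women".
- **Section 17, Aim 2 design paragraph.** It opens with "We will recruit 320 pregnant women between 20-34 weeks of gestation". Later in the same paragraph: "Participants will be randomized (1:1) to receive the postpartum care system (175) or standard of care (175" per arm.
- **Section 12, Local Number of Participants.** "Based on prior studies at Grady, we assume a recruitment rate of 50% and expect to approach approximately 640 women".
- **Section 9, Study Timelines.** From about 200 deliveries a month, 40% eligible, 15% without prenatal care and 50% agreeing, "we expect recruitment to take about 9 months".
- **Section 6, Data collection.** The primary outcome, attendance at the postpartum visit, "will be identified using data from the medical record".

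The total of 320 also stands in section 1 (Sample Size), section 2 (Aim 2) and section 13. The figure of 175 per arm appears only in section 17.

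**The concern.** Two figures in the sample-size statement disagree with the plan's own inputs.

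First, the target of 320 is presented as the result of inflating 292 for loss of up to 15%, and no usual inflation gives that number. Second, a 1:1 split of 320 is 160 per arm, not 175. Neither simple randomization (section 17) nor minimization (section 5) can make the planned arms add up to 30 more than the planned total.

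At stake is whether a reader can say how many women were planned and how much loss was allowed for. The planned number is the yardstick for judging whether enrolment was completed. The data and safety monitoring board also reviews enrolment and attrition (section 18) and needs a single target to review against.

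**Working it through.** **Inputs.** From section 17: 292 evaluable (146 per arm), loss up to 15%, target 320, arms 175 and 175, attendance 55% versus 78%, risk ratio 1.5. From section 12: 640 approached, 50% agreeing. From section 9: 200 deliveries a month, 40% eligible, 15% without prenatal care, 50% agreeing, about 9 months.

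**Step 1: try to reproduce 320.**
- Standard inflation, N/(1 − d): 292/0.85 = 343.5, so 344 (172 per arm).
- Shortcut, N × (1 + d): 292 × 1.15 = 335.8, so 336.
- Neither gives 320. The target is 24 below the first and 16 below the second.

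**Step 2: what 320 does cover.**
- Loss that still leaves 292: 1 − 292/320 = 8.75%.
- Evaluable at 15% loss: 320 × 0.85 = 272 (136 per arm), which is 20 women or 7% short of 292.

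**Step 3: the arms.**
- 175 + 175 = 350, which is 30 women (9%) more than 320.
- At 15% loss, 350 × 0.85 = 297.5, so 350 would meet the stated allowance. It covers loss up to 1 − 292/350 = 16.6%.

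**Step 4: which total fits the other planning figures.**
- Approached: 640 × 0.50 = 320, whereas 350 would need 350/0.50 = 700.
- Accrual: 200 × 0.40 × 0.85 × 0.50 = 34 a month. Then 320/34 = 9.4 months and 350/34 = 10.3 months, against a stated figure of about 9.

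The recruitment figures fit 320, while the 15% allowance fits 350.

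**Step 5: effect on power.** The plan states neither alpha nor a test for its power calculation. The figures below assume a two-sided alpha of 0.05 and the normal approximation for two proportions, 55% versus 78%.

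| Evaluable per arm | Uncorrected | Continuity-corrected |
|---|---|---|
| 146 (292 in all) | 98.8% | 98.4% |
| 136 (272 in all) | 98.3% | 97.7% |
| 73 (one of two equal strata, 292 in all) | 84.5% | 79.8% |
| 68 (one of two equal strata, 272 in all) | 81.8% | 76.5% |

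The last two rows matter only if the even stratification by chronic or new-onset disease means that each stratum was powered separately. At the plan's other stated effect, a risk ratio of 1.5 (0.55 × 1.5 = 82.5%), 68 per arm gives 94.2% uncorrected and 91.6% corrected.

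**The case against.** The strongest reply is that the arithmetic is wrong but little hangs on it. The planned primary analysis is one pooled comparison adjusted for diagnosis, and its power barely moves between 292 and 272 evaluable. No within-stratum test is planned. The only figure that falls clearly below 80% (76.5%) needs a within-stratum reading, a continuity correction, an assumed alpha and 78% rather than the stated risk ratio. Attendance comes from the medical record, so a missed survey need not lose the primary outcome. All of this stands, and it limits the weight of the point.

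Two qualifications apply. The plan itself applies the 15% to this sample size. Under section 14, records of women who withdraw are abstracted only for the period in which they were enrolled, so loss on the primary outcome is not necessarily zero.

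A second reply is that 15% is a ceiling, so 320 suffices if loss is lower. That is true up to 8.75%. Beyond that, the target fails within the range the sentence allows.

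A third is that 320 appears in several sections and 175 in only one, so the 175s look like the slip. That is a fair inference, but 350 is the total that meets the 15% allowance, and the document does not say which figure was intended.

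A fourth is that 292 itself is an uncertain base: pooled power at 146 per arm is about 99%, not 80%, and 78% against 55% is a risk ratio of 1.42, not 1.5. That is a reason to restate the power calculation, not a defence of 320.

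**Conclusion.** The concern holds on both counts. The target of 320 cannot be obtained from 292 evaluable women and 15% loss; 344 is needed, or 336 by the shortcut. As written, 320 covers 8.75% loss and leaves 272 at 15%. Separately, the planned arms add up to 350, and nothing reconciles that with 320. These findings rest on the plan's own numbers and need no outside assumption.

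The point is one of arithmetic and consistency in the sample-size statement. It does not show that the primary comparison is underpowered. Under the assumed two-sided alpha of 0.05, pooled power at 15% loss stays near 98%. It should be fixed because the planned sample size and loss allowance are wrong as stated and the correction is cheap.

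**What to change.** State one total and arm sizes that add up to it.

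- **If 320 is intended:** change both 175s in section 17 to 160. Then state either that 320 allows for up to about 8.75% loss, or that 15% loss leaves 272 evaluable (136 per arm). In the second case, recompute power by the sponsor's own method, giving alpha and the test. This costs restated figures only and needs no extra participants.
- **If 350 is intended:** correct 320 in sections 1, 2, 12, 13 and 17, and the figures derived from it: 640 approached becomes 700, and about 9 months becomes about 10.

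Moving to 344 or 350 would mean 24 to 30 more women and 48 to 60 more approached. At the planned 34 a month that is under one month (30/34 = 0.9), provided enrolment is still open. The document does not say whether it is, and the latest entry in its revision history refers to data already collected, so restating the figures is the first remedy to consider.

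Under either option, the Power paragraph should say how 292 was obtained, including what the even stratification by disease type contributes.
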